Patients will return to centers for IGA, lesion counts, PRO questionnaire, , Investigator Cutaneous Safety Assessment and Local Tolerability Assessments at Weeks 2, 4, 8 and 12. At Week 12 (or at the early termination visit) patients will be asked to complete RosaQoL questionnaire. Adverse events and concomitant medications will be assessed throughout the treatment period. A urine pregnancy test is required at Visit 1, 2, 4, 5 and 6 for all females of child-bearing potential.

Clinical Evaluations will be performed at:

- Visit 1/Screening
- Visit 2/Baseline, Day 1
- Visit 3/Week 2, Day 15 ( $\pm$  3 Days)
- Visit 4/Week 4, Day 29 ( $\pm$  3 Days)
- Visit 5/Week 8, Day 57 ( $\pm$  3 Days)
- Visit 6/Week 12, Day 85 ( $\pm$  4 Days)/End of Treatment)

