## 13.9. Study Flow Chart

Procedures	Visit 1 	Visit 2 	Visit 3 	Visit 4 	Visit 5 	Visit 6  (EOT  / EOS  )
Name of Visit	Screening -35 – 0	Baseline Day 1	Week 2 Day 15	Week 4 Day 29	Week 8 Day 57	Week 12 Day 85
Visit window			± 3 days	± 3 days	± 3 days	± 4 days
Informed Consent	X					
Demographics	X					
Medical History/Previous Therapies	X	X				
Brief Physical Examination		X				X
Inclusion/Exclusion Criteria	X	X				
Urine Pregnancy Test 	X	X		X	X	X
IGA	X	X	X	X	X	X
Inflammatory Lesion Counts	X	X	X	X	X	X
Assessment of Eligibility		X				
Rosacea Erythema Assessment		X	X	X	X	X
Telangiectasia Assessment		X	X	X	X	X
Randomization		X				
Cutaneous Safety Assessment and Local Tolerability Assessments		X	X	X	X	X
Administer/ Review Patient Instructions		X	X	X	X	
Weigh Study Product		X		X	X	X
Study Product Dispensed		X 		X	X	
Provide Cleanser and Moisturizer/Sunscreen 		X				
Diary Card dispensed		X		X	X	
Study Product Collected				X	X	X
Diary Card collected				X	X	X
Patient Compliance Reviewed (Diary)			X	X	X	X
Concomitant Therapy and Medication History Reviewed	X	X	X	X	X	X
Adverse Events	X 	X	X	X	X	X
Photography (select site(s))		X	X	X	X	X
Complete PAPSS, PAPI and PGI-S 		X	X	X	X	X
Complete PGI-C, PGI-TS and PGI-SE 			X	X	X	X
Complete RosaQoL 		X				X

 If no washout is needed, Visits 1 and 2 may occur on the same day. If a washout is needed, Visit 2 must occur within 35 days of Visit 1.

 All visit dates are in reference to Baseline, e.g., Visit 5 occurs 8 weeks ± 3 days after Baseline Visit.

 All Week 12 procedures should be completed for Patients who terminate early.

 EOT – end of treatment

 EOS – end of study

 All women of childbearing potential

 Dispense one pump of test material at the Baseline Visit and dispense additional pump at Visit 4 and 5.

 Or study approved cleanser and moisturizer

 Adverse events after ICF is signed will be collected.

 PAPSS is Patient Assessment of Papulopustular rosacea Signs and Symptoms; PAPI is Patient Assessment of Papulopustular rosacea Impacts; PGI-S is Patient Global Impression of Symptom Severity. Questionnaires will be completed prior to PI assessment.

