8.1.3 Visit Windowing

Data will be summarized based on nominal visit indications with the exception of data captured at early termination and unscheduled visits. Data from early termination and unscheduled visits will be summarized based on mapped visit values. The analysis windows for early termination and unscheduled visits are presented in the following table.

Analysis Windows for Efficacy and Safety Assessments

Scheduled Visit	Target Study Day	Window (Days)
Week 2	15	8 to 21
Week 4	29	22 to 42
Week 8	57	43 to 70
Week 12	85	71 to 98

Data collected at early termination and unscheduled visits prior to study day 8 will not be analyzed, with the exception of those identified as Baseline values. Data collected at early termination and unscheduled visits after study day 98 will not be included in analyses.

The definition for the study day included in each study window is defined as below:

Study Day prior to Day 1 = Visit Date – Day 1 Date

Study Day on or after Day 1 = Visit Date – Day 1 Date + 1

If an assessment's mapped visit is a visit at which the subject has data from a scheduled visit present, or if no analyses are planned for the assessment at the mapped visit, the data collected at the early termination or unscheduled visit will not be included in analyses.

In the event of multiple values from unscheduled or early termination assessments within an analysis window, the value closest to the scheduled visit target study day will be used for analyses. If two values tie as closest to the time point (for example, one value is before and the other value is after the time point), then the later value will be selected.

Data collected at all visits will be included in the data listings with visit presented as reported by the site.

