8.8.4.4 Physical Examination

Abnormal physical examination findings will be summarized by body system, visit, and treatment group. In addition to the summary, all physical examination findings will be listed.

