SOURCE: USERNAME\SPONSOR\PROJECT\JOBNAME (DATE, TIME)

Table 14.3.1.4.1: Summary of Vital Signs
(Safety Population)
(Page 4 of 5)

Diastolic Blood Pressure (mmHg)	E-BPO 5% Cream (N=xxx)	Vehicle Cream (N=xxx)
Baseline		
n	xxx	xxx
Mean	xx.x	xx.x
SD	xx.xx	xx.xx
Median	xx.x	xx.x
Min. to Max.	xx to xx	xx to xx
Week 12		
n	xxx	xxx
Mean	xx.x	xx.x
SD	xx.xx	xx.xx
Median	xx.x	xx.x
Min. to Max.	xx to xx	xx to xx
Change from Baseline		
n	xxx	xxx
Mean	xx.x	xx.x
SD	xx.xx	xx.xx
Median	xx.x	xx.x
Min. to Max.	xx to xx	xx to xx

Note: No imputation of missing values. Negative change values represent decrease from Baseline.

SOURCE: USERNAME\SPONSOR\PROJECT\JOBNAME (DATE, TIME)

Table 14.3.1.4.1: Summary of Vital Signs
(Safety Population)
(Page 5 of 5)

Heart Rate (beats/min)	E-BPO 5% Cream (N=xxx)	Vehicle Cream (N=xxx)
Baseline		
n	xxx	xxx
Mean	xx.x	xx.x
SD	xx.xx	xx.xx
Median	xx.x	xx.x
Min. to Max.	xx to xx	xx to xx
Week 12		
n	xxx	xxx
Mean	xx.x	xx.x
SD	xx.xx	xx.xx
Median	xx.x	xx.x
Min. to Max.	xx to xx	xx to xx
Change from Baseline		
n	xxx	xxx
Mean	xx.x	xx.x
SD	xx.xx	xx.xx
Median	xx.x	xx.x
Min. to Max.	xx to xx	xx to xx

Note: No imputation of missing values. Negative change values represent decrease from Baseline.

SOURCE: USERNAME\SPONSOR\PROJECT\JOBNAME (DATE, TIME)

Table 14.3.1.4.2: Shift Table of Vital Signs
(Safety Population)

	E-BPO 5% Cream (N=xxx)			Vehicle Cream (N=xxx)		
Systolic Blood Pressure (mmHg)	Week 12			Week 12		
Baseline	<90 mmHg	90-140 mmHg	>140 mmHg	<90 mmHg	90-140 mmHg	>140 mmHg
<90 mmHg	xx (xx.x%)	xx (xx.x%)	xx (xx.x%)	xx (xx.x%)	xx (xx.x%)	xx (xx.x%)
90-140 mmHg	xx (xx.x%)	xx (xx.x%)	xx (xx.x%)	xx (xx.x%)	xx (xx.x%)	xx (xx.x%)
>140 mmHg	xx (xx.x%)	xx (xx.x%)	xx (xx.x%)	xx (xx.x%)	xx (xx.x%)	xx (xx.x%)
Diastolic Blood Pressure (mmHg)	Week 12			Week 12		
Baseline	<90 mmHg	90-100 mmHg	>100 mmHg	<90 mmHg	90-100 mmHg	>100 mmHg
<90 mmHg	xx (xx.x%)	xx (xx.x%)	xx (xx.x%)	xx (xx.x%)	xx (xx.x%)	xx (xx.x%)
90-100 mmHg	xx (xx.x%)	xx (xx.x%)	xx (xx.x%)	xx (xx.x%)	xx (xx.x%)	xx (xx.x%)
>100 mmHg	xx (xx.x%)	xx (xx.x%)	xx (xx.x%)	xx (xx.x%)	xx (xx.x%)	xx (xx.x%)
Heart Rate (beats/min)	Week 12			Week 12		
Baseline	<60 bpm	60-100 bpm	>100 bpm	<60 bpm	60-100 bpm	>100 bpm
<60 mmHg	xx (xx.x%)	xx (xx.x%)	xx (xx.x%)	xx (xx.x%)	xx (xx.x%)	xx (xx.x%)
60-100 mmHg	xx (xx.x%)	xx (xx.x%)	xx (xx.x%)	xx (xx.x%)	xx (xx.x%)	xx (xx.x%)
>100 mmHg	xx (xx.x%)	xx (xx.x%)	xx (xx.x%)	xx (xx.x%)	xx (xx.x%)	xx (xx.x%)

Note: No imputation of missing values.

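### The SAP's visit-mapping rule leaves early leavers' only scheduled post-baseline vital signs and physical examination out of the safety summary tables

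*SAP*

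**What the plan says.** **Collection.** In the flow chart (Protocol 5.2 and 13.9) the brief physical examination is marked only at Visit 2 and Visit 6. Protocol 13.7 makes vital signs part of that examination. Footnote 3 of the flow chart adds: "All Week 12 procedures should be completed for Patients who terminate early". Protocol 13.14 lists the examination under the visit that serves as Week 12, end of treatment or early termination.

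**Mapping.** SAP 8.1.3 summarises scheduled visits by their nominal label but treats early termination (ET) differently: "Data from early termination and unscheduled visits will be summarized based on mapped visit values". The windows are Days 8–21 (Week 2), 22–42 (Week 4), 43–70 (Week 8) and 71–98 (Week 12). For very early visits, "Data collected at early termination and unscheduled visits prior to study day 8 will not be analyzed", apart from values identified as Baseline. ET values after Day 98 are also left out. Finally, "if no analyses are planned for the assessment at the mapped visit, the data collected at the early termination or unscheduled visit" is not included in analyses.

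**Reporting.** SAP 8.8.4.4 says: "Abnormal physical examination findings will be summarized by body system, visit, and treatment group". SAP 8.8.4.3 likewise promises vital signs by visit. Neither section names the visits. The shells do: Table 14.3.1.4.1 (vital-sign values and changes), "Table 14.3.1.4.2: Shift Table of Vital Signs" and Table 14.3.1.5 (abnormal examination findings) contain only Baseline and Week 12. SAP 8.1.5 says safety data other than incomplete medication dates are not imputed.

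**Listings.** SAP 8.1.3 also says: "Data collected at all visits will be included in the data listings with visit presented as reported by the site".

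**The concern.** For a patient who leaves before the Week 12 window, the ET visit is the only scheduled occasion after Baseline on which vital signs and the examination are recorded. The protocol asks for that visit. The general windowing rule then moves its values to a week at which the shells have no place for them, and so removes them from the summaries.

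The three tables would describe change and abnormality only in patients seen around Week 12. Patients who left early, among them those who stopped for adverse events, would count in the Safety-population denominator but contribute no post-baseline value. A safety summary that is selective in this way is least informative about the patients of most interest.

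The effect also looks unintended. Protocol 19.6.1 promises vital signs and their changes at every applicable visit, and SAP section 10, which lists departures from the protocol's analyses, does not mention this exclusion.

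**Working it through.** **1. The windows.** Target days are 1, 15, 29, 57 and 85. The midpoints are (1+15)/2 = 8, (15+29)/2 = 22, (29+57)/2 = 43 and (57+85)/2 = 71. These reproduce the four lower bounds in SAP 8.1.3, so the Day 71 cut-off is read correctly.

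**2. The rule applied to each possible ET day.** Week 12 is the only post-baseline visit at which these two assessments are tabulated.

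| ET visit on study day | Number of days | Mapped to | Vital signs and examination summarised? |
|---|---|---|---|
| 1–7 | 7 | not analysed | no |
| 8–21 | 14 | Week 2 | no, none planned |
| 22–42 | 21 | Week 4 | no, none planned |
| 43–70 | 28 | Week 8 | no, none planned |
| 71–98 | 28 | Week 12 | yes |
| after 98 | – | excluded | no |

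The first four rows sum to 7 + 14 + 21 + 28 = 70 days, and none of them reaches Week 12. Because safety data are summarised as observed, nothing replaces the missing values.

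**3. Possible size.** The planned number randomised is 234 + 117 = 351 (Protocol 19.1.4). The documents give no dropout rate, so three things are assumed: an overall rate of 5%, 10% or 20%; withdrawals spread evenly over Days 2–84; and an ET visit for every leaver, on the day of withdrawal.

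- Share of withdrawal days before Day 71: Days 2–70 are 69 days and Days 2–84 are 83 days, so 69/83 = 0.83.
- 5%: 351 × 0.05 × 0.83 ≈ 15 patients.
- 10%: 351 × 0.10 × 0.83 ≈ 29 patients.
- 20%: 351 × 0.20 × 0.83 ≈ 58 patients.

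At each assumed rate and timing these are upper figures. Patients lost to follow-up, and some who withdraw consent, will have no ET visit and so no values to exclude.

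**The case against.** The rule is explicit and pre-specified. Keeping a value taken after one to ten weeks of exposure out of a row labelled Week 12 is defensible. That stands, and it is why the Week 12 row should stay as it is. It does not explain why the value should appear in no summary at all.

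SAP 8.8.4.3 and 8.8.4.4 say only that results are given by visit, so the restriction to Week 12 rests on the shells and the protocol schedule. Table 14.0.2.1 also uses a combined Week 12/ET label, which could suggest that the two share one visit record. This is fair, but SAP 8.1.3 expressly takes ET data out of nominal-visit summaries. At most it shows that two programmers could produce different tables, which is itself a reason to clarify.

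Several stronger readings are tempting, and the documents do not support them:

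- **That the data are lost.** They are not. Listings 16.2.8.2 and 16.2.8.3 keep the examination and vital signs by subject.
- **That early leavers disappear from the safety evaluation.** Adverse events are tabulated, including those leading to discontinuation. Dryness, scaling, itching and burning/stinging are summarised at Weeks 2, 4, 8 and 12, so mapped ET values have a place to go.
- **That everyone who stops before Day 71 is excluded.** The rule uses the date of the ET visit. A patient who stops on Day 66 and attends on Day 72 maps to Week 12.
- **That RosaQoL has the same fault.** The protocol does collect it at ET: "At Week 12 (or at the early termination visit) patients will be asked to complete RosaQoL questionnaire". However, Protocol 19.4.5 and SAP 7.1.4 define the exploratory endpoint as change from Baseline to Week 12. Omitting a Day 40 value follows that definition, and no text says that ET collection was meant to feed it.

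**Conclusion.** The point holds for vital signs and physical examination, and only for the summary tables. As written, any ET visit before Day 71 or after Day 98 contributes no post-baseline value to Tables 14.3.1.4.1, 14.3.1.4.2 and 14.3.1.5.

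The number of patients concerned is unknown. The figures of at most about 15, 29 or 58 illustrate assumed dropout of 5%, 10% or 20% and depend on even timing and full ET attendance; they are not forecasts.

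No primary or secondary analysis, hypothesis test or sample-size figure is touched. These tables are descriptive, and the protocol's named safety endpoints are adverse events and the cutaneous and tolerability scores. This is a low-cost improvement that makes three safety tables less selective. It is not a flaw that threatens the trial's conclusions.

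**What to change.** In SAP 8.1.3, add a sentence exempting vital signs and physical examination recorded at an ET visit from the mapping rule and from the Day 8 and Day 98 limits. Add an end-of-treatment row, defined as Week 12 or early termination, to Tables 14.3.1.4.1 and 14.3.1.5, and the corresponding panel to Table 14.3.1.4.2. Keep the Week 12 results unchanged beside it. If the sponsor does intend the exclusion, the SAP should say so and give the reason.

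The cost is one sentence and one added row or panel in three tables. No new data are needed, and the blind, the error rate and the endpoints are unaffected. The added row mixes different lengths of exposure; the retained Week 12 row offsets that. RosaQoL may stay as planned, and an end-of-treatment row there is optional.

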8.1.4 Adjustments for Covariates

Baseline lesion count will be a covariate for the primary efficacy endpoint for lesion counts. No other covariates are planned to be used in the analyses for this study.

8.1.5 Handling of Dropouts or Missing Data

Missing data for the ITT population will be estimated by multiple imputation and subsequently analyzed. Missing lesion count and IGA data will be derived for the analysis using the method of Markov Chain Monte Carlo (MCMC) multiple imputation. The pattern of missing observations in each treatment group cannot influence the missing value estimation in the other group because the imputation will be conducted independently for each treatment group.

Last observation carried forward (LOCF) will be used to impute missing data for the efficacy analyses using the PP population.

Patients that discontinue from the study due to an AE related to study treatment or documented lack of treatment effect will be included in the PP population. Data for these subjects will not be imputed by multiple imputation or LOCF but rather their data will be imputed with values consistent with their status as treatment failures. For these subjects, values for lesion count and IGA will be imputed such that change from Baseline is zero, meaning the values will be set to the Baseline value. This imputation will be done after the data for all subjects has been through the MI process.

Incomplete start and end dates for medications will be imputed. Other safety data will not be imputed and will be summarized on an observed case basis.

8.1.5.1 Lesion Count Variable Missing Data Imputation

Multiple imputation and subsequent analysis will involve 3 distinct phases with these principal tasks:

1. Create a data set of patients, one for each treatment group, with observed values and those needing estimation by MCMC. The missing lesion count values in each data set will be filled in using the MCMC method 5 times to generate 5 data sets. The resulting data sets for each treatment arm will be combined into one complete data set for each imputation.

Syntax:

```
proc mi data=datain out=dataout seed=&seed. nimpute=5 <options>;  
  where trtpn=(1, or 2);  
  mcmc chain=multiple;  
  var baseline week2 week4 week8 week12;  
run;
```

2. For each complete data set, the variable of interest for Baseline minus the value for the week imputed will be computed. Each complete data set will be analyzed as specified for the particular analysis.
3. The results from these analyses will be combined into a single inference using SAS PROC MIANALYZE.

A total of 2 random seeds are needed to impute inflammatory lesion counts. These random seeds have been pre-specified by using a random number generator:

- Inflammatory Lesion Counts S5G4T-1: Seed = 2046620966
- Inflammatory Lesion Counts Vehicle: Seed = 693843173

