8. STATISTICAL AND ANALYTICAL PLANS

8.1 General Methodology

All statistical processing will be performed using SAS® version 9.3 or later unless otherwise stated. Statistical significance will be based on two-tailed tests of the null hypothesis resulting in p-values of 0.05 or less. These methods are intended to analyze the results of the study.

The primary method of handling missing efficacy data will be based on estimation using the method of Markov Chain Monte Carlo (MCMC) imputation. This method provides robust estimation when the pattern of missingness is arbitrary. Additionally, the estimation will be done for each treatment group separately so that the pattern of missingness for one group does not influence the estimation of missing data for another group. Groups of complete datasets following the estimation will be concatenated to form analysis datasets for the comparative analyses and subsequent imputation result inference with SAS PROC MIANALYZE.

Descriptive statistics will also be derived from the multiply imputed datasets.

Additionally, a model-based multiple imputation process will be used as a sensitivity analysis to the MCMC imputation. Finally, the absolute change in lesion count will be analyzed using a repeated measures analysis of covariance (ANCOVA) for lesion count data and a repeated measures logistic regression model (generalized estimating equations) for the dichotomized IGA.

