8.1.5.2 IGA Missing Data Imputation

A similar procedure will be used for the analyses based on proportion of IGA successes wherein the ANCOVA analysis is replaced with a logistic regression analysis. Specifically, missing IGA values from which the dichotomized IGA is derived will be estimated by MCMC.

The pattern of missing observations in each treatment group cannot influence the missing value estimation in the other because the imputation is being conducted independently for each treatment group.

The missing IGA values will be derived for the analysis using the method of MCMC multiple imputation. Multiple imputation and subsequent analysis will involve 3 principal tasks:

1. Create a data set, one for each treatment group, of patients with observed values and those needing estimation by MCMC. The missing IGA values in each data set will be filled in using the MCMC method 5 times to generate 5 data sets. The resulting data sets for each treatment arm will be combined into one complete data set by imputation.

Syntax:

```
proc mi data=datain out=dataout seed=&seed. nimpute=5 <options>;  
  where trtpn=(1, or 2);  
  mcmc chain=multiple;  
  var baseline week2 week4 week8 week12;  
run;
```

2. For each complete data set, the dichotomous success rate (clear or almost clear) will be computed. The estimated global values will be rounded to the nearest integer value prior to evaluating the success rate. Each complete data set will be analyzed with a logistic regression with factors of treatment group and analysis center.
3. The results from these analyses will be combined into a single inference using SAS PROC MIANALYZE.

A total of 2 random seeds will be needed to impute IGA for the two treatment groups. Those 2 random seeds have been pre-specified by using a random number generator:

- IGA Week S5G4T-1: Seed = 712066910
- IGA Week Vehicle: Seed = 1200150465

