8.1.8 Multiple Comparisons/Multiplicity

In testing the secondary efficacy endpoints the overall Type I error will be controlled by requiring the two co-primary efficacy endpoints to be statistically significant. Specifically, failure of either one of the primary efficacy endpoints will invalidate the statistical significance of the secondary efficacy endpoints.

A stepwise process will be conducted for testing the secondary efficacy endpoints in order to control for multiplicity. These tests will be performed for only the ITT population. The testing process will terminate whenever a statistical test for a step is not significant. All subsequent tests for the remaining steps will be considered not significant. The order of testing is provided below.

Step Number	Secondary Endpoint
1	Percent change in inflammatory lesion count from Baseline to Week 12
2	Absolute change in inflammatory lesion count from Baseline to Week 8
3	Proportion of patients with the primary measure of success “Clear” (0) or “Almost clear” (1) in the IGA relative to Baseline at Week 8
4	Absolute change in inflammatory lesion count from Baseline to Week 4
5	Proportion of patients with the primary measure of success “Clear” (0) or “Almost clear” (1) in the IGA relative to Baseline at Week 4

In testing the supportive efficacy endpoints, the overall Type I error will be controlled by the Benjamini-Hochberg method. The Hochberg and Bejamini adaptive step-down Bonferoni method will be used within PROC MULTTEST in SAS (AHOLM option in PROC MULTTEST).

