8.7.2 Sensitivity Efficacy Analysis

8.7.2.1 Sensitivity Analyses for Absolute Change in Lesion Count

The first sensitivity analysis for absolute change in lesion count will use a repeated measures ANCOVA, with treatment, analysis center, visit (i.e., Weeks 2, 4 and 8), and treatment group by visit interaction as independent factors and a covariate of Baseline lesion count. In this analysis, data from all post-baseline visits will be included with no imputation for missing data.

The second sensitivity analysis will use the model based multiple imputation method to impute missing data for the absolute change in lesion counts at Week 12. The multiple imputation will involve 3 principal tasks:

1. Missing values will be filled in 5 times to generate 5 complete data sets. The imputation model used will be an ANCOVA with factors of treatment group and analysis center, and a covariate of Baseline lesion count (i.e., the imputation model will be the same as the analysis model).

Syntax:

```
proc mi data=datain out=dataout seed=&seed. nimpute=5 <options>;  
  class trtpn sitegr1;  
  var trtpn baseline sitegr1 week12;  
  monotone logistic (sitegr1=trtpn baseline);  
  monotone reg (week12=trtpn baseline sitegr1);  
run;
```

2. Each complete data set will be analyzed with an ANCOVA with factors of treatment group, and analysis center, and a covariate of Baseline lesion count. Appropriate modifications will be made should the analysis be based on a non-parametric method.
3. Results from these analyses will be combined into a single inference.

One random seed will be needed to impute the inflammatory lesion counts. The following random seed has been pre-specified by using a random number generator:

Inflammatory Lesion Count Seed=1543491304

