The protocol describes imputing only Week 12 data with MCMC imputation, but all missing post-baseline data will be imputed. Only 2 seeds are needed for the MCMC imputation for inflammatory lesions (one seed for S5G4T-1 and one seed for vehicle) so only the Week 12 seeds from the protocol were used in the SAP. Only 2 seeds are needed for the MCMC imputation for IGA (one seed for S5G4T-1 and one seed for vehicle) so only the Week 12 seeds from the protocol were used in the SAP. Using only the Week 12 seed addresses concern from the FDA with regard to imputing data at each visit as the multiple seeds in the protocol suggests. Only one seed is needed for treatment group as PROC MI will impute data across the visits.

Geographic region was removed from the examination of subgroups as all sites in the study are in the United States.

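### Five imputations per analysis is low and unjustified for confirmatory tests: the co-primary verdicts are nearly unaffected at the planned effects, but a secondary result near 0.05 could turn on the seed

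*SAP*

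**What the plan says.** For the ITT lesion-count analysis, SAP 8.1.5.1 has missing values "filled in using the MCMC method 5 times to generate 5 data sets", and its PROC MI call sets nimpute=5. SAP 8.1.5.2 does the same for the other co-primary: "The missing IGA values in each data set will be filled in using the MCMC method 5 times to generate 5 data sets". For lesion counts, "The results from these analyses will be combined into a single inference using SAS PROC MIANALYZE"; 8.1.5.2 pools the IGA results in the same way. The model-based sensitivity analysis of lesion counts in 8.7.2.1 repeats the number ("Missing values will be filled in 5 times to generate 5 complete data sets"), as does the IGA counterpart in 8.7.2.2. Protocol 19.4.7 and 19.4.8 also use five.

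The secondary endpoints inherit this. SAP 8.7.3 applies the primary methods to them, the planned secondary table carries the MCMC note, and Section 10 states that "all missing post-baseline data will be imputed", so Weeks 4, 8 and 12 all rest on the same five data sets.

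On seeds, 8.1.5.1 states: "These random seeds have been pre-specified by using a random number generator". There is one per arm for each endpoint.

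On decisions, 8.1 states: "Statistical significance will be based on two-tailed tests of the null hypothesis resulting in p-values of 0.05 or less". Under 8.1.8, "failure of either one of the primary efficacy endpoints will invalidate the statistical significance of the secondary efficacy endpoints", and the secondary sequence stops at the first step that fails.

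Neither document explains the choice of five, gives an expected dropout or missing-data rate, or plans a check on Monte Carlo error.

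**The concern.** Five imputations give good relative efficiency for a point estimate, but these analyses end in p-values compared with a hard limit. With m = 5 the between-imputation variance is estimated on 4 degrees of freedom, so the pooled estimate, its standard error and its reference distribution all vary with the seed. In a fixed sequence, a step that fails by chance of the seed also removes every later claim. The skewness p-value that selects ranked or unranked ANCOVA at 0.01 is likewise an average over the same five data sets (footnote to planned Table 14.2.1.2). That effect was not quantified here.

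**Working it through.** **1. The plan's own figures.** SAP Section 9 gives IGA rates of 53.3% and 20.0%, with 86/43 patients for 95% power. A two-proportion calculation with continuity correction returns 86/43. For lesions it gives a difference of 14.1 − 7.4 = 6.7, with SDs 6.70 and 17.24. At 200/100 the standard error is √(6.70²/200 + 17.24²/100) = √3.197 = 1.788, so the noncentrality is 3.75. An unequal-variance t-test then has 96.0% power against the stated 95%. Both reproduce.

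**2. Planned effects at 234/117.**
- Lesions: 6.7/√(6.70²/234 + 17.24²/117) = 6.7/√2.732 = 4.05.
- IGA, log-odds scale: ln(0.533/0.467) − ln(0.20/0.80) = 1.518; standard error √(1/(234×0.533×0.467) + 1/(117×0.20×0.80)) = 0.266; z about 5.7.

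**3. Model for seed noise.** Scale the total variance to 1 and let γ be the fraction of missing information. Write z for the statistic that unlimited imputations would give. Within-imputation variance is W = 1 − γ. Over seeds:
- pooled estimate ~ N(z, γ/m);
- between-imputation variance B ~ γ·χ²(m−1)/(m−1);
- T = W + (1 + 1/m)B, with Rubin degrees of freedom (m−1)[1 + W/((1 + 1/m)B)]².

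At γ = 0.10 the seed SD of the pooled estimate is √(0.10/5) = 0.141 with m = 5 and √(0.10/100) = 0.032 with m = 100. The relative error of B is √(2/4) = 71% against √(2/99) = 14%. By simulation, the test statistic has a seed SD of 0.16 against 0.035.

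γ is an assumption throughout, because the documents give no missing-data rate. The range shown is 5% to 20%.

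**4. A result near the limit** (z = 2.2, p = 0.028):

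| γ | seeds with p > 0.05, m = 5 | m = 100 |
|---|---|---|
| 5% | about 2% | none |
| 10% | about 11% | none |
| 15% | about 19% | none |
| 20% | about 25% | essentially none |

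The central 95% range of p with m = 5 is 0.016 to 0.049 at γ = 5% and 0.013 to 0.067 at γ = 10%. With m = 100 at 10% it is 0.023 to 0.033. For a result at p = 0.04 with γ = 5%, 10% and 20%, the share of seeds giving p ≤ 0.05 is 78%, 66% and 56% with m = 5; 99.7%, 97% and 88% with m = 50; and 100%, 99.6% and 96% with m = 100.

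**5. A result at the planned lesion effect** (z = 4.05, m = 5). The central 95% range of p reaches 0.0007 at γ = 10% and 0.0038 at γ = 20%. Virtually no seed crosses 0.05.

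**6. Over repeated trials.** Two different seeds would disagree on significance as follows (noncentrality is for complete data, reduced by √(1 − γ); γ = 5%, 10%, 20%):
- noncentrality 4.05: 0.7%, 1.5%, 3.9% of trials with m = 5, against 0.1%, 0.3%, 0.6% with m = 100;
- noncentrality 2.8, a weaker step with about 80% power: 3.7%, 6.0%, 11.0%, against 0.8%, 1.3%, 2.1%.

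**7. Error rates.** Simulated type I error with m = 5 is about 5%. With noncentrality 2.8 on the fully imputed scale, power is about 79.6%, 78.9% and 77.0% at γ = 5%, 10% and 20%, against about 80% with m = 100.

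**8. Patient-level check.** This used 234/117 patients, monotone dropout, within-arm imputation and ANCOVA on treatment and baseline. Visit SD 12 and autoregressive correlation 0.75 were assumed, and centre was omitted. With the 6.7-lesion difference every seed was significant. In simulated trials with p of about 0.04, 91%, 68%, 66% and 63% of m = 5 seeds gave p ≤ 0.05 at 5%, 10%, 15% and 20% dropout.

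**The case against.** A reader might infer that the co-primary p-values depend materially on the seed, that the error rate is compromised, or that a favourable seed could be chosen. The documents support none of these. The seeds are written into the SAP, so each analysis has one reproducible p-value. Rubin's degrees of freedom allow for finite m and hold the type I error. On the plan's own assumptions both co-primaries lie far from the limit.

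The missing-information range is also assumed. With Weeks 2, 4 and 8 in the imputation model, missing information is usually below the dropout rate. At 5% even a result at z = 2.2 crosses in only about 2% of seeds. The repeated-measures ANCOVA and the GEE in 8.7.2 use no imputation and so give seed-free checks on both co-primaries.

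All of this stands, and it limits the point to noise and a small power loss. It does not justify five. The seed-free analyses are sensitivity analyses and do not replace the primary test, and 8.7.2 does not cover the secondary steps. The planned effects come from Phase 2 arms of 30 to 32 patients, and no power is stated for Week 4 or Week 8. Fixing the seed makes the draw reproducible but does not make it representative.

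**Conclusion.** The point holds as a cheap improvement. Five imputations are used, without justification, for both ITT co-primaries, all five gated secondary tests and the model-based sensitivity analyses. At the planned effects the co-primary verdicts are nearly seed-proof. The exposure is a result near 0.05, which is more plausible at the Week 4 and Week 8 steps. There the seed could decide the step and every step after it, with a power loss of roughly 0.4 to 3 percentage points for a step powered at about 80%. These sizes rest on assumed missing information of 5% to 20%; below that range the effect is smaller still. There is no bias, no inflation of type I error and no scope for choosing a seed afterwards.

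**What to change.** Before unblinding, set nimpute=100 (50 at the least) in the PROC MI calls of SAP 8.1.5.1, 8.1.5.2, 8.7.2.1 and 8.7.2.2, amend the matching text, and keep the pre-specified seeds. Because protocol 19.4.7 and 19.4.8 also state five, record the difference and its reason in SAP Section 10. The imputation models, analysis models, alpha and order of testing do not change.

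The cost is trivial computing time and one documented protocol–SAP difference. The SAP preface allows updates until the blind is broken. It also says that a protocol amendment will be considered for major differences affecting the primary endpoint, so the sponsor should note its judgement on that. Section 10 records regulatory feedback on the seeds, and keeping them leaves that point untouched.
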